3.1.5 End of treatment phase

When the investigator documents that the last dose of oliceridine was administered and that the patient will no longer be treated with oliceridine, the treatment phase is complete and the end of treatment phase begins. A physical examination will be performed at this time.

Within 1 hour after completion of the treatment phase, vital signs, oxygen saturation, and somnolence/sedation will be measured, and concomitant medications and AEs/SAEs will be recorded.

Within 3 hours after completion of the treatment phase, blood will be collected for clinical laboratory tests. Concomitant medications and AEs/SAEs will be recorded.

Trevena, Inc.

Protocol CP130-3003

Version 5.0

14 Sep 2016

Patients will be observed for at least three hours after the last dose of oliceridine; however, medically-required transfer of an ED patient to another facility takes precedence over study procedures.

The Subjective Opioid Withdrawal Scale (SOWS) will be administered to detect symptoms of opioid withdrawal. If the patient is discharged or transferred before the time when the SOWS is to be performed, it will be performed one day after completion of the treatment phase and returned to the site by mail or in person.

3.1.6 Follow up phase

A follow up contact will be made between 2 and 3 days after completion of the treatment phase. The contact may be conducted in person or by telephone. Concomitant medications and AEs/SAEs will be recorded.

The surgical procedure, medical diagnosis or ED diagnosis for which parenteral opioid therapy was warranted will be captured using the International Classification of Diseases, 10th Revision (ICD-10) terminology.

3.2 Study Duration

The duration of treatment for each patient will be determined by the clinical need for parenteral opioid therapy. In current practice, parenteral opioids are used as-needed for up to several days. Although preclinical toxicology studies support IV administration of oliceridine for up to 14 days, it is unlikely that patients will receive oliceridine for that duration in the context of this study.

3.3 Study Population

The study population consists of patients with moderate to severe acute pain for which parenteral opioid therapy is warranted.

3.3.1 Inclusion Criteria

Patients must meet all the inclusion criteria:

1. Age \geq 18 years at screening.
2. Moderate to severe acute pain for which parenteral opioid therapy is warranted, defined as NPRS pain intensity of \geq 4 during the pre-dose period.
3. Able to understand and comply with the procedures and study requirements, and to provide written informed consent before any study procedure.

Trevena, Inc.

Protocol CP130-3003

Version 5.0

14 Sep 2016

4. If it is anticipated that the patient will be treated with oliceridine in the ED with subsequent discharge or transfer to another facility, that the patient will remain under the care of the investigator for at least three hours after the last dose of oliceridine.

3.3.2 Exclusion Criteria

Given that the primary objective of this study is to evaluate the safety and tolerability of oliceridine in patients with moderate to severe acute pain for which parenteral opioid therapy is warranted, imprudent inclusion of unsuitable patients that would unduly increase patient risk or confound the evaluation of oliceridine is not acceptable. The stated exclusion criteria are not exhaustive and prudent clinical judgment must be applied.

Patients must not meet any of the following exclusion criteria:

1. Participated in another oliceridine clinical study.
2. Clinically significant medical, surgical, postsurgical, psychiatric or substance abuse condition or history of such condition that would confound the interpretation of safety, tolerability, or efficacy data in the study.
3. Hemodynamic instability or respiratory insufficiency; or requires a tracheostomy or mechanically assisted ventilation.
4. If a surgical or medical patient, American Society of Anesthesiologists (ASA) Physical Status Classification System score of IV or worse (see [Section 9.3](#)) ([American Society of Anesthesiologists, 2014](#)); if an ED patient, Emergency Severity Index (ESI) triage score of 1 (see [Section 9.4](#)) ([Gilboy, 2011](#)).
5. If an ED patient, alcohol intoxication, acute substance impairment or positive urine or serum toxicology screen.
6. Advanced cancer in palliative or end-of-life care.
7. Concurrent use of chemotherapeutic or biologic agents for the treatment of cancer.
8. Another current painful condition (other than acute pain for which parenteral opioid therapy is warranted) that would confound the interpretation of safety, tolerability, or efficacy data in the study.
9. Clinically significant, immune-mediated hypersensitivity reaction to opioids.
10. Pregnancy, breastfeeding, or positive urine or serum pregnancy test at screening.
11. Hepatic impairment (total bilirubin $>2 \times$ upper limit of normal [ULN], aspartate aminotransferase [AST] $\geq 1.5 \times$ ULN AND alanine aminotransferase [ALT] $\geq 1.5 \times$ ULN) or renal impairment (estimated Glomerular Filtration Rate [eGFR] ≤ 29 mL/min/1.73 m² based on the Modification of Diet in Renal Disease [MDRD] equation), known or obtained at screening ([Levey, 2009](#)).

Trevena, Inc.

Protocol CP130-3003

Version 5.0

14 Sep 2016

12. History of human immunodeficiency virus, hepatitis B, or hepatitis C.
13. Clinically significant abnormal clinical laboratory values, known or obtained at screening.
14. Clinically significant abnormal electrocardiogram (ECG), including a QT interval corrected for heart rate (Fridericia; QTcF interval) of >450 msec in males and >470 msec in females, known or obtained at screening.

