	
data in the study.
 
9. Clinically significant, immune-mediated hypersensitivity reaction to opioids.
 
10. Pregnancy, breastfeeding, or positive urine or serum pregnancy test at screening.
 
11. Hepatic impairment (total bilirubin $>2 \times$ upper limit of normal [ULN], aspartate aminotransferase [AST] $\geq 1.5 \times$ ULN AND alanine aminotransferase [ALT] $\geq 1.5 \times$ ULN) or renal impairment (estimated Glomerular Filtration Rate [eGFR] ≤ 29 mL/min/1.73 m² based on the Modification of Diet in Renal Disease [MDRD] equation), known or obtained at screening.
 
12. History of human immunodeficiency virus, hepatitis B, or hepatitis C.
 
13. Clinically significant abnormal clinical laboratory values, known or obtained at screening.
 
14. Clinically significant abnormal ECG, including a QT interval corrected for heart rate (Fridericia; QTcF interval) of >450 msec in males and >470 msec in females, known or obtained at screening.

--	---

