listed in the above definition. These should also be considered serious. Examples of such events are invasive or malignant cancers, intensive treatment in an emergency room or at home for allergic bronchospasm, blood dyscrasias or convulsions that do not result in hospitalization, or development of drug dependency or drug abuse.

Note that the terms “serious” and “severe” ARE NOT synonymous. The term “severe” is often used to describe the intensity (severity) of a specific event (as in mild, moderate, or severe myocardial infarction); the event itself, however, may be of relatively minor medical significance (such as a severe headache). This is NOT the same as “serious,” which is based on patient/event outcome or action criteria described above and are usually associated with events that pose a threat to a patient’s life or functioning. A severe AE does not necessarily need to be considered serious. For example, persistent nausea of several hours duration may be considered severe nausea but not an SAE. On the other hand, a stroke resulting in only a minor degree of disability may be considered mild but would be defined as an SAE based on the above noted criteria. Seriousness (not severity) serves as a guide for defining regulatory reporting obligations.

4.1.3 Clinical Laboratory Abnormalities and Other Abnormal Assessments as Adverse Events and Serious Adverse Events

Abnormal laboratory findings (eg, clinical chemistry, hematology, and urinalysis) or other abnormal assessments (eg, vital signs) that are judged by the investigator as clinically significant will be recorded as AEs or SAEs, if they meet the definition of an AE or SAE. Clinically significant abnormal laboratory findings or other abnormal assessments that are detected during the study or are present at baseline and significantly worsen from time of informed consent will be reported as AEs or SAEs.

The investigator will exercise his or her medical and scientific judgment in deciding whether an abnormal laboratory finding or other abnormal assessment is clinically significant.

[figure not shown]

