Liver chemistry thresholds have been designed to assure patient safety. When patients meet the hepatic transaminase threshold criteria (AST or ALT $\geq 3 \times$ ULN), the patient should undergo close observation, including monitoring for symptoms (clinical symptoms of hepatitis or hypersensitivity, fatigue, decreased appetite, nausea, vomiting, abdominal pain, jaundice, fever, or rash) and hepatic function (AST, ALT, alkaline phosphatase, and fractionated bilirubin) at least every 48 hours, until symptoms and/or hepatic function abnormalities resolve, stabilize, or return to baseline values. This event must be reported to Trevena within 24 hours of learning of its occurrence.

[Figure 2](#) represents the decision tree for whether or not IP will be discontinued.

Specialist or hepatology consultation should be considered in cases of protocol-mandated IP discontinuation.

Figure 2: Monitoring of Patients with Elevated Hepatic Transaminases

Liver Function Abnormalities

Trevena, Inc.

Protocol CP130-3003

Version 5.0

14 Sep 2016

In addition, every attempt must be made to obtain the following for any patient who meets the hepatic transaminase threshold criteria:

- Viral hepatitis serology including:
 - Hepatitis A immunoglobulin M (IgM) antibody.
 - Hepatitis B surface antigen and hepatitis B core antibody (IgM).
 - HCV RNA.
 - Cytomegalovirus IgM antibody.
 - Epstein-Barr viral capsid antigen IgM antibody (or if unavailable, obtain heterophile antibody or monospot testing).
 - Hepatitis E IgM antibody (if patient resides outside the USA or Canada, or has traveled outside USA or Canada in past 3 months).
- Serum creatine phosphokinase and LDH.
- Record the appearance or worsening of clinical symptoms of hepatitis, or hypersensitivity, fatigue, decreased appetite, nausea, vomiting, abdominal pain, jaundice, fever, or rash, as relevant, on the AE report form.
- Record the use of concomitant medications, including acetaminophen, herbal remedies, other over the counter medications, putative hepatotoxins, or alcohol on the concomitant medications report form.
- The following are required for patients with AST or ALT $\geq 3 \times$ ULN and bilirubin $\geq 2 \times$ ULN but are optional for other abnormal liver chemistries:
 - Anti-nuclear antibody, anti-smooth muscle antibody, and type 1 anti-liver kidney microsomal antibodies.
 - Liver imaging (ultrasound, magnetic resonance, or computerized tomography) to evaluate liver disease.

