<T30 Minutes>	xxx (xxx.x)	xxx (xxx.x)	xxx (xxx.x)	xxx (xxx.x)	xxx (xxx.x)	xxx (xxx.x)
Normal	xxx (xxx.x)	xxx (xxx.x)	xxx (xxx.x)	xxx (xxx.x)	xxx (xxx.x)	xxx (xxx.x)
Abnormal, NCS	xxx (xxx.x)	xxx (xxx.x)	xxx (xxx.x)	xxx (xxx.x)	xxx (xxx.x)	xxx (xxx.x)
Abnormal, CSig	xxx (xxx.x)	xxx (xxx.x)	xxx (xxx.x)	xxx (xxx.x)	xxx (xxx.x)	xxx (xxx.x)
Missing	xxx (xxx.x)	xxx (xxx.x)	xxx (xxx.x)	xxx (xxx.x)	xxx (xxx.x)	xxx (xxx.x)
...						

Note: NCS = Not clinically significant; CSig = Clinically significant.

Clinical significance is based on the investigator interpretation as recorded.

Percentages are based on the number of patients with a non-missing baseline and post-baseline windowed time point value within each windowed time point, parameter and cumulative dose group.

Worst post-baseline is calculated as the most extreme absolute change from baseline value.

Trevena, Inc.
Protocol CP130-3003

CONFIDENTIAL
Page x of y

- [a] See section 6.2.3 of the SAP for windowed time point intervals.
- [b] Baseline is the last non-missing value prior to the patient receiving the first dose of oliceridine.

Programmer's Note: Continue with all parameters and all windowed time points even if all counts are 0.

Use the same template as for Table 14.3.3.1.2 for the following tables:

Table 14.3.3.2.2
Clinically Significant Clinical Laboratory Chemistry Results
(Safety Analysis Set)

Table 14.3.4.1
Select Hepatic Laboratory Findings on Treatment
(Safety Analysis Set)

Windowed Time Point [a] Test Result	Oliceridine <= 4 mg N=XXX n (%)	Oliceridine >4 to 8 mg N=XXX n (%)	Oliceridine >8 to 16 mg N=XXX n (%)	Oliceridine >16 to 36 mg N=XXX n (%)	Oliceridine >36 mg N=XXX n (%)	All Treated Patients N=XXX n (%)
Patients with at Least 1 Hepatic Laboratory Finding						
AST >=3 X ULN	xxx (xxx.x)	xxx (xxx.x)	xxx (xxx.x)	xxx (xxx.x)	xxx (xxx.x)	xxx (xxx.x)
ALT >=3 X ULN	xxx (xxx.x)	xxx (xxx.x)	xxx (xxx.x)	xxx (xxx.x)	xxx (xxx.x)	xxx (xxx.x)
AST or ALT >=3 X ULN	xxx (xxx.x)	xxx (xxx.x)	xxx (xxx.x)	xxx (xxx.x)	xxx (xxx.x)	xxx (xxx.x)
AST >=5 X ULN	xxx (xxx.x)	xxx (xxx.x)	xxx (xxx.x)	xxx (xxx.x)	xxx (xxx.x)	xxx (xxx.x)
ALT >=5 X ULN	xxx (xxx.x)	xxx (xxx.x)	xxx (xxx.x)	xxx (xxx.x)	xxx (xxx.x)	xxx (xxx.x)
AST or ALT >=5 X ULN	xxx (xxx.x)	xxx (xxx.x)	xxx (xxx.x)	xxx (xxx.x)	xxx (xxx.x)	xxx (xxx.x)
BILI >=2 X ULN	xxx (xxx.x)	xxx (xxx.x)	xxx (xxx.x)	xxx (xxx.x)	xxx (xxx.x)	xxx (xxx.x)
<T30 Minutes>						
AST >=3 X ULN	xxx (xxx.x)	xxx (xxx.x)	xxx (xxx.x)	xxx (xxx.x)	xxx (xxx.x)	xxx (xxx.x)

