ALT >=3 X ULN	xxx (xxx.x)	xxx (xxx.x)	xxx (xxx.x)	xxx (xxx.x)	xxx (xxx.x)	xxx (xxx.x)
AST or ALT >=3 X ULN	xxx (xxx.x)	xxx (xxx.x)	xxx (xxx.x)	xxx (xxx.x)	xxx (xxx.x)	xxx (xxx.x)
...						

Note: ALT = Alanine Aminotransferase; AST = Aspartate Aminotransferase; BILI = Total Bilirubin; ULN = Upper Limit of Normal.

Percentages are based on the number of patients with a non-missing windowed time point value within each windowed time point and cumulative dose group.

[a] See section 6.2.3 of the SAP for windowed time point intervals.

Programmer's Note: Continue with all windowed time points and criteria rows, even if all counts are 0..

Table 14.3.5.1
Change from Baseline in Vital Signs
(Safety Analysis Set)

Parameter (unit) Windowed Time Point [a]	Baseline/ Observed/ Change from Baseline	Oliceridine						All Treated Patients N=XXX		
		<= 4 mg N=XXX	>4 to 8 mg N=XXX	>8 to 16 mg N=XXX	>16 to 36 mg N=XXX	>36 mg N=XXX				
<Parameter x (unit)>										
<Baseline [b]>										
n	Observed	xxx	xxx	xxx	xxx	xxx	xxx	xxx		
Mean (SD)		xx.x (x.xx)	xx.x (x.xx)	xx.x (x.xx)	xx.x (x.xx)	xx.x (x.xx)	xx.x (x.xx)	xx.x (x.xx)		
Median		xx.x	xx.x	xx.x	xx.x	xx.x	xx.x	xx.x		
Min, Max		xx, xx	xx, xx	xx, xx	xx, xx	xx, xx	xx, xx	xx, xx		
<T30 Minutes>										
n	Baseline [c]	xxx	xxx	xxx	xxx	xxx	xxx	xxx		
Mean (SD)		xx.x (x.xx)	xx.x (x.xx)	xx.x (x.xx)	xx.x (x.xx)	xx.x (x.xx)	xx.x (x.xx)	xx.x (x.xx)		
Median		xx.x	xx.x	xx.x	xx.x	xx.x	xx.x	xx.x		
Min, Max		xx, xx	xx, xx	xx, xx	xx, xx	xx, xx	xx, xx	xx, xx		
n	Observed	xxx	xxx	xxx	xxx	xxx	xxx	xxx		
Mean (SD)		xx.x (x.xx)	xx.x (x.xx)	xx.x (x.xx)	xx.x (x.xx)	xx.x (x.xx)	xx.x (x.xx)	xx.x (x.xx)		
Median		xx.x	xx.x	xx.x	xx.x	xx.x	xx.x	xx.x		
Min, Max		xx, xx	xx, xx	xx, xx	xx, xx	xx, xx	xx, xx	xx, xx		
n	Change	xxx	xxx	xxx	xxx	xxx	xxx	xxx		
Mean (SD)		xx.x (x.xx)	xx.x (x.xx)	xx.x (x.xx)	xx.x (x.xx)	xx.x (x.xx)	xx.x (x.xx)	xx.x (x.xx)		
Median		xx.x	xx.x	xx.x	xx.x	xx.x	xx.x	xx.x		
Min, Max		xx, xx	xx, xx	xx, xx	xx, xx	xx, xx	xx, xx	xx, xx		
...										

[a] See section 6.2.3 of the SAP for windowed time point intervals.

[b] Baseline is the last non-missing value prior to the patient receiving the first dose of oliceridine.

[c] Only patients with both a baseline value and a windowed time point value are summarized at a given windowed time point. *Programmer's Note: Repeat Parameter (unit) in each page if it wraps on to multiple pages.*

Table 14.3.5.2
Change from Baseline in Oxygen Saturation (%)
(Safety Analysis Set)

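### SAP Table 14.3.4.1 counts on-treatment hepatic threshold findings without regard to baseline, and exclusion criterion 11 alone does not keep out patients who start above a threshold

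*Protocol*

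**What the plan says.** **Analysis.** SAP 6.3.3 and 8.6.4 define hepatic thresholds: AST, ALT, and either enzyme, at or above 3 × and 5 × ULN, and bilirubin at or above 2 × ULN. They are tabulated by cumulative dose group and time point in mock Table 14.3.4.1, "Select Hepatic Laboratory Findings on Treatment". The table note says "Percentages are based on the number of patients with a non-missing windowed time point value". Neither the text nor the shell conditions on baseline. The shell runs from the overall rows straight to the first post-dose window.

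**Entry.** Criterion 11 (Protocol 3.3.2, repeated in the synopsis) lists total bilirubin above 2 × ULN, then a comma, then "aspartate aminotransferase [AST] $\geq 1.5 \times$ ULN AND alanine aminotransferase [ALT] $\geq 1.5 \times$ ULN". Criterion 13 also excludes "Clinically significant abnormal clinical laboratory values, known or obtained at screening", with no numeric limit. Section 4.1.3 leaves clinical significance to the site: "The investigator will exercise his or her medical and scientific judgment in deciding whether an abnormal laboratory finding" is significant.

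**Safety threshold.** Section 4.1.3 uses either enzyme, not both: "When patients meet the hepatic transaminase threshold criteria (AST or ALT $\geq 3 \times$ ULN), the patient should undergo close observation".

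**Sampling.** The protocol schedules one post-dose laboratory sample, within 3 hours after the treatment phase ends (Section 3.1.5, Table 2). SAP 4.1 also mentions laboratory blood during dosing. SAP 6.2.4 summarises end-of-treatment laboratory values in addition to the windowed ones.

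**The concern.** Safety is the primary objective, every patient receives oliceridine, and there is no comparator against which to judge background liver abnormalities. The baseline value is the only control a patient has. A table of threshold findings that ignores baseline mixes elevations that began after dosing with elevations the patient brought in. With small counts, a few of the second kind could dominate a row.

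The SAP does use baseline elsewhere. QTcF is categorised by change from baseline (SAP 6.3.5), and an adverse event must be new or worsened to be treatment-emergent (SAP 6.3.2). Under Protocol 4.1.3, a laboratory abnormality present at baseline is reportable as an adverse event only if it significantly worsens. The hepatic table is out of line with all three.

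**Working it through.** The plan gives no figure to reproduce on this point. The check has four steps: entry logic, table logic, the other displays, and an illustration of size.

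**1. Can a patient pass criterion 11 while above a hepatic threshold?** The comma before AST allows several readings. I ran each over 147 combinations: bilirubin 1.0, 2.0 and 2.1 × ULN; AST and ALT each 1.0, 1.4, 1.5, 2.0, 2.9, 3.0 and 5.0 × ULN (3 × 7 × 7 = 147). This tests logic and does not estimate prevalence.

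| Patient is excluded if | Not excluded | Of these, AST or ALT ≥ 3 × ULN | Of these, AST or ALT ≥ 5 × ULN |
|---|---|---|---|
| bilirubin OR (AST AND ALT) | 48 | 16 | 8 |
| (bilirubin OR AST) AND ALT | 62 | 20 | 10 |
| bilirubin AND AST AND ALT | 122 | 56 | 30 |

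AST 3.2 ×, ALT 1.2 ×, bilirubin 1.0 × ULN passes criterion 11 on all three readings and already meets the Section 4.1.3 threshold. AST 6 × with ALT 1.4 × ULN also passes on all three and meets the 5 × row. The readings also disagree with one another: both enzymes at 1.5 × ULN with normal bilirubin is excluded on the first two and not on the third.

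**2. What does the table do with such a patient?** Take two patients, both of whom pass criterion 11 if the other enzyme and bilirubin are normal.

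- Patient A: ALT 6 × ULN at baseline, 3.1 × after dosing. The value has fallen, but A is counted in the ALT ≥ 3 × row.
- Patient B: ALT 1.2 × ULN at baseline, 6 × after dosing. B is counted in the ≥ 3 × and ≥ 5 × rows.

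The ≥ 3 × row treats A and B alike.

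**3. Does another planned display separate them?**

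- Chemistry shift table (14.3.3.2.1): categories are Low, Normal and High, cross-tabulated against baseline. A and B are both High-to-High. A Normal-to-High patient is identifiable as new, but 1.1 × and 6 × ULN share the High category.
- Change-from-baseline summaries: group statistics, with no threshold crossing per patient.
- Clinical-significance table (14.3.3.2.2): has a baseline row, but the categories are investigator interpretation, and the baseline and later rows are separate counts.
- Listing 16.2.7.1: gives each value with its date, time and window but has no ULN or reference-range column. Laboratories are local, with local ranges (Protocol 3.6.2.6), so a reader cannot work out multiples of ULN from the listing.

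**4. Illustrative size.** Let q be the share of treated patients who enter at or above 3 × ULN and are still there after dosing, and i the true new-onset rate among the rest. The table shows q + (1 − q)·i. Both inputs are assumptions; i is set at 0.2% and N at 1000.

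| q | Pre-existing patients (1000·q) | Rate shown |
|---|---|---|
| 0.1% | 1 | 0.001 + 0.999 × 0.002 = 0.30% |
| 0.5% | 5 | 0.005 + 0.995 × 0.002 = 0.70% |
| 1% | 10 | 0.010 + 0.990 × 0.002 = 1.20% |
| 2% | 20 | 0.020 + 0.980 × 0.002 = 2.20% |

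For scale, 0 of 1000 has a one-sided 95% upper bound of 1 − 0.05^(1/1000) = 0.30%. Restricting the count to patients below the threshold at baseline returns 0.2% in every row.

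**The case against.** Several arguments on the other side are sound and limit what can be claimed.

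- A reader might infer that patients above 3 × ULN are eligible. The documents do not say so. Passing criterion 11 is not entry: criterion 13 may exclude them, and the preamble to the exclusions says the list is not exhaustive and asks for clinical judgement. These safeguards are discretionary, so they reduce the number but set no limit.
- A reader might infer that no planned display tells old elevations from new. The shift table does so at the upper limit of normal. It fails only at 3 × and 5 × ULN.
- A reader might infer that criterion 11 and Section 4.1.3 contradict each other. An entry limit and a monitoring trigger serve different purposes. Section 4.1.3 does not confine its threshold to post-dose values, and the decision tree in Figure 2 is not available here, so a baseline condition there cannot be ruled out.
- A reader might infer that AND is a slip for OR. It is capitalised, it is the same in the synopsis and the body, and it fits the deliberately broad population in Section 1.2. Nothing supports replacing it.
- The table is labelled on treatment, not emergent, and the adverse event rules handle worsening. That is true, but those rules depend on the investigator's judgement of significance. The threshold table is the display that does not.
- Screening values may be up to 14 days old and laboratories are scheduled again at baseline, so a raised baseline can occur under any wording of criterion 11. This shows that the table problem does not depend on the AND.

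**Conclusion.** The point holds for the table. As specified, Table 14.3.4.1 counts a patient who was above a hepatic threshold before dosing as an on-treatment finding if the value is still raised, and no other planned display sorts this out at 3 × or 5 × ULN. Criterion 11 makes such patients possible because no reading of it excludes an isolated rise in one transaminase. Its punctuation also leaves unclear whether bilirubin stands alone or belongs to the AND.

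The size is unknown. The 1 to 20 patients per 1000 rest on an assumed 0.1% to 2% who enter and remain above the threshold. They also assume that the post-dose sample feeds the table, which the SAP leaves open. Severity is moderate: no hypothesis test is affected, but the counts belong to the primary safety objective. The documents do not support saying that such patients will be enrolled in any particular number, or that one entry limit is the right one.

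**What to change.** **SAP.** In Table 14.3.4.1 report each threshold by baseline status. Patients below the threshold at baseline who reach it after dosing are new onset, with patients below it at baseline as the denominator. Patients at or above it at baseline go in a separate row. State whether the end-of-treatment sample feeds the table; it is the only post-dose laboratory sample the protocol schedules, so the table's content depends on the answer. The cost is one derivation and one extra row, from data already collected.

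**Protocol.** Reword criterion 11, in the synopsis and Section 3.3.2, so that it has one reading, and reconcile it with the either-enzyme threshold in Section 4.1.3. Which entry limit applies is for the sponsor to decide. The cost is a one-line clarification.

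The SAP change is worth making whatever is decided about criterion 11.
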